## 1.6 Leptomeningeal Carcinomatosis

With increased utilization of postoperative SRS in place of WBRT and expanding data on outcomes, specific patterns of CNS failure are becoming clearer. A number of studies report excellent local control rates with postoperative SRS (up to 83 to 94% at 24 months) but with distant intracranial failure rates of 40 to 60% within 12 months. This is consistent with previously published data demonstrating inferior distant brain control with SRS compared to SRS with adjuvant WBRT.

Of increasing interest is the incidence of leptomeningeal carcinomatosis in patients with solid tumors and brain metastases. Rates of leptomeningeal disease with solid tumors are reported to be in the range of 5 to 15%. Risk factors for leptomeningeal involvement include breast cancer histology (particularly triple-negative receptor status and infiltrating lobular carcinoma), as well as non-small cell lung cancer and melanoma histologies. Treatment options at the time of leptomeningeal failure typically include radiation, intrathecal chemotherapy, and/or systemic chemotherapy depending on histology. Prognosis with leptomeningeal metastasis is poor, with reported survival in the range of two to six months.

Neurosurgical risk factors for leptomeningeal carcinomatosis include piecemeal resection, opening of the ventricular system, and infratentorial lesions. In the setting of up-front surgery, the hypothesis is that any anatomic disruption that allows cerebrospinal fluid (CSF) contamination with tumor cells may predispose for leptomeningeal spread. Although postoperative SRS

provides excellent local control at the resection cavity, it does not address tumor cells that have seeded the CSF. Currently reported rates of leptomeningeal failure after surgery with postoperative SRS for brain metastases are in the range of 8 to 24%.

In 2016, Johnson et al. reported significantly greater incidence of leptomeningeal metastasis with surgery followed by SRS in comparison to SRS alone (16.9% vs. 5.2%,  $p<.01$ ). Ma et al. published similar findings, reporting a 6.5 times higher odds of leptomeningeal disease in patients who were treated with surgical resection prior to SRS. A recently published abstract by Prabhu et al. describes a “nodular” pattern of leptomeningeal spread associated with surgery followed by SRS that is distinct from the classic “sugarcoated” pattern of leptomeningeal carcinomatosis described in other settings. The authors also reported more favorable survival with the nodular pattern and that SRS may be a feasible option for focal treatment of nodular leptomeningeal disease. Adjuvant WBRT may offset the risk of leptomeningeal disease some degree, although this does not address the entire volume of CSF circulation.

## 1.7 Study Rationale

Given the increased risk of leptomeningeal failure with surgery followed by SRS, as well as the risk of radiation necrosis, new paradigms in therapy delivery and sequencing are being explored. Areas of investigation include optimization of target volume, marginal expansion, multifractionation, timeliness of SRS after surgery, and delivery of SRS prior to surgical resection. In theory, advantages of preoperative SRS include better target delineation, sterilization of tumor cells prior to surgical disruption of the tumor, vascular supply, and CSF spaces, and resection of tissue that would otherwise be at risk of radiation necrosis.

In 2014, Asher et al. reported that the use of neoadjuvant SRS prior to surgery was both safe and effective (even for metastases  $>3$  cm) with no reported leptomeningeal recurrences or radiation necrosis. More recently, Patel et al. performed a retrospective comparison of preoperative versus postoperative SRS and reported no difference in local control, distant brain failure, or overall survival. Furthermore, the authors reported significantly lower rates of leptomeningeal carcinomatosis and radiation necrosis with preoperative SRS.

Huff et al. recently published a protocol for a phase II prospective trial designed to compare outcomes using preoperative SRS versus historically cited outcomes for postoperative SRS. Our current pilot study mirrors this design and aims to confirm study feasibility and to assess local control, CNS progression-free survival, overall survival, rates of leptomeningeal spread, rates of radiation necrosis, and quality of life measures with the use of preoperative SRS.

# 2 HYPOTHESIS, OBJECTIVES, AND ENDPOINTS

Our hypothesis is that preoperative GK-SRS is feasible and results in greater local control than postoperative radiosurgery to the resection cavity.

## 2.1 Primary Objectives

1. To assess feasibility of preoperative GK-SRS in patients with brain metastases treated with preoperative GK-SRS.
2. To assess local control in patients with brain metastases treated with preoperative GK-SRS.

## **2.2 Secondary Objective(s)**

1. To assess survival (CNS progression-free survival and overall survival) for patients undergoing preoperative SRS and surgical resection.
2. To document rates of leptomeningeal carcinomatosis for patients undergoing preoperative SRS and surgical resection.
3. To record incidence of radiation necrosis in patients undergoing preoperative GK-SRS and surgical resection.
4. To document quality of life measures using preoperative GK-SRS and to compare to historically cited rates using postoperative GK-SRS.

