## **2.3 Primary Endpoint**

1. Feasibility for this study will be defined as 50% of enrolled study subjects undergoing the surgical resection as per the protocol.
2. Measure rate of local control at the resection cavity any new tumors by post-treatment MRI.

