## **2.4 Secondary Endpoint(s)**

1. CNS progression-free survival and overall survival will be evaluated at six, 12, and 18 months following surgical resection.
2. Rates of leptomeningeal carcinomatosis using preoperative GK-SRS will be documented and compared to historically cited rates for postoperative GK-SRS.
3. Incidence of radiation necrosis will be measured by post-treatment MRI.
4. Quality of life measures will be collected and will be compared to historically cited data.

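### Secondary objectives are framed in resected patients and survival is timed from resection, so subjects irradiated but not resected have no survival time zero and no settled place in the necrosis and leptomeningeal denominators

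*Combined protocol and SAP*

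**What the plan says.** Three secondary objectives in Section 2.2 (repeated in the Protocol Summary) name patients who have both procedures:

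- Survival: "To assess survival (CNS progression-free survival and overall survival) for patients undergoing preoperative SRS and surgical resection".
- Leptomeningeal disease: "To document rates of leptomeningeal carcinomatosis for patients undergoing preoperative SRS and surgical resection".
- Necrosis: "To record incidence of radiation necrosis in patients undergoing preoperative GK-SRS and surgical resection".

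Section 2.4 sets the survival clock: "CNS progression-free survival and overall survival will be evaluated at six, 12, and 18 months following surgical resection".

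Other parts of the plan are wider. The primary objectives in Section 2.1 refer to patients treated with preoperative GK-SRS and do not mention resection. The other two endpoints in Section 2.4 read "Rates of leptomeningeal carcinomatosis using preoperative GK-SRS will be documented and compared to historically cited rates for postoperative GK-SRS" and "Incidence of radiation necrosis will be measured by post-treatment MRI"; neither is limited to resected patients. Section 3.2 begins with enrolled patients receiving SRS and then lists survival, leptomeningeal disease and necrosis as outcomes to be documented and compared with historical rates. Section 7 defines no analysis set and no time origin.

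**The concern.** The intervention is a sequence: radiosurgery first, resection one to 10 days later. Not reaching surgery is a possible cost of that order, and the feasibility criterion allows for it: "Feasibility for this study will be defined as 50% of enrolled study subjects undergoing the surgical resection as per the protocol". An outcome restricted to resected patients is conditioned on having got through the interval.

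This matters most for necrosis. Section 1.7 lists among the theoretical advantages of preoperative SRS the "resection of tissue that would otherwise be at risk of radiation necrosis". On that reasoning, the irradiated but unresected subject keeps the tissue at risk, yet objective 3 leaves that subject out. For survival, a subject with no resection date cannot be placed on the clock at all. For necrosis and leptomeningeal disease, the objective and the endpoint imply different denominators, so two analysts could follow the plan and report different rates from the same data.

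**Working it through.** The plan gives no figure for this point. Its one precision statement (Section 7.1) concerns local control and does not bear on it. The check sets the passages side by side and then bounds the size.

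**Who is counted, as written**

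| Outcome | Objective (2.2) | Endpoint (2.4) | Irradiated, not resected |
|---|---|---|---|
| CNS-PFS, OS | SRS and resection | from resection | no time zero; excluded |
| Leptomeningeal disease | SRS and resection | no resection condition | conflict |
| Radiation necrosis | SRS and resection | no resection condition | conflict |

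**What else captures these events.** Section 4.6 keeps subjects who stop study treatment in follow-up with study procedures. Section 6.2.1 records grade 3 to 5 adverse events and all serious events from consent, and Section 6.1.2 counts death as serious. The Study Calendar marks adverse event reporting at the radiosurgery and resection visits. Events in the interval that meet those criteria are therefore recorded. However, collection stops 30 days after the last dose of a study drug (this trial has none), and the calendar marks no adverse event reporting in follow-up. Later necrosis in an unresected subject may be visible on a follow-up MRI and still fall outside both objective 3 and adverse event collection.

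**How many subjects.** Enrolment is up to 15 (Protocol Summary).

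- The 50% criterion needs 0.5 × 15 = 7.5, so 8 resected. That leaves up to 15 − 8 = 7 unresected (47%).
- If 10 of 15 are resected, 5 are unresected (33%). The 10 is borrowed from the target for completed subjects, which is a different concept.
- Assumption: all of these received SRS. The documents give no expected number.

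**Chance of at least one necrosis event among them**, 1 − (1 − r)^n. The upper rate is the 23% ceiling in Section 1.5. The lower is 4%, the bottom of the 4 to 20 per 100 band in which the SRS side-effect list places severe damage to, or death of, normal brain tissue.

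| r | n = 5 | n = 7 |
|---|---|---|
| 4% | 1 − 0.96^5 = 0.18 | 1 − 0.96^7 = 0.25 |
| 23% | 1 − 0.77^5 = 0.73 | 1 − 0.77^7 = 0.84 |

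**Effect on a reported rate** (illustration with no events in 10 resected subjects; exact binomial 95% intervals):

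- Resected only: 0/10 (0 to 0.3085).
- All 15 irradiated, with 0, 1 or 2 events among the 5 unresected: 0/15 (0 to 0.2180), 1/15 = 6.7% (0.0017 to 0.3195), 2/15 = 13.3% (0.0166 to 0.4046).
- Survival: one death before surgery, with 10 resected subjects all alive at a landmark, changes 10/10 to 10/11 = 90.9%.

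**Effect of the clock alone.** Moving time zero to SRS shifts it by at most 10 days. With 30.4375 days per month, that is 10/182.6 = 5.5% of six months, 10/365.25 = 2.7% of 12 months and 10/547.9 = 1.8% of 18 months. This is minor; who is counted matters more.

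**The case against.** The strongest reply is that this is a descriptive pilot aiming for 10 completed subjects, and that the wider passages already do most of the work. A reader of Section 2.2 alone might infer that harms in unresected subjects, or between SRS and surgery, are never counted and would show only as a lower feasibility percentage. The documents do not support that. Two of the endpoints are unrestricted, follow-up continues after treatment stops, and interval deaths and severe events are recorded. Table 2 sends grade 4 and 5 serious events to the DSMC within five calendar days, and Section 8.4 lets the DSMC terminate the study if it is unsafe. This part of the reply stands. Even so, recording an event as serious does not place it in a survival or necrosis estimate.

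A reader might also infer that the comparison with historical rates is biased in favour of the new sequence. That cannot be shown. The comparator is postoperative SRS, whose patients had also undergone surgery and gone on to SRS, and the documents give neither its denominator nor its time origin. The resected subset may be the closer match, which is a reason to keep it as a display.

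The counts of 5 and 7 are also open to challenge. Enrolment is dated from confirmation of eligibility (Section 4.1) and treatment may start up to 14 days later, so some unresected subjects may never be irradiated. Eligibility requires that surgery be possible within one to 10 days. The 23% is a ceiling, and a subject who dies before surgery does not carry the full necrosis risk. This stands too, so the figures are a range under assumptions and not a forecast.

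**Conclusion.** The point holds as a conflict over who is analysed and from when. Followed literally, the plan gives an irradiated but unresected subject no survival time zero and keeps a death or progression before surgery out of every survival estimate. It also leaves two incompatible denominators for necrosis and leptomeningeal disease. Later necrosis in an unresected subject is the weakest spot.

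The size depends on a number the documents do not give. If 5 to 7 of 15 subjects were irradiated and not resected, at least one necrosis event among them has a probability anywhere from 18% to 84%, depending mainly on the assumed rate. If nearly all irradiated subjects reach surgery, the numerical effect is small, but the wording still needs to be settled before the data are seen.

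**What to change.** In Sections 2.2, 2.4 and 7.2 (and the Protocol Summary), define an analysis set of all subjects who receive any GK-SRS. Report necrosis, leptomeningeal disease, CNS-PFS and OS in that set, timed from the SRS date (calendar Day 1). Keep the resected subset, timed from resection, as a supporting display for the historical comparison.

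Two further changes are needed for this to work:

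- **Section 7.3.** It removes subjects who do not complete follow-up from all primary and secondary objectives. Unless amended, it would still drop early deaths and exits from the new set. State that these are counted as events or censored, and not excluded.
- **Study Calendar.** Follow-up is counted to 18 months from the post-surgical resection visit, which is unclear for a subject without surgery. Anchor it to the SRS date for unresected subjects; the one-month visit is already timed from radiosurgery.

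The cost is mainly wording. Section 4.6 already keeps these subjects on study procedures, so little extra assessment should be needed. The downside is that the survival and toxicity figures may look slightly less favourable.

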## **2.3 Primary Endpoint**

1. Feasibility for this study will be defined as 50% of enrolled study subjects undergoing the surgical resection as per the protocol.
2. Measure rate of local control at the resection cavity any new tumors by post-treatment MRI.

## **2.4 Secondary Endpoint(s)**

1. CNS progression-free survival and overall survival will be evaluated at six, 12, and 18 months following surgical resection.
2. Rates of leptomeningeal carcinomatosis using preoperative GK-SRS will be documented and compared to historically cited rates for postoperative GK-SRS.
3. Incidence of radiation necrosis will be measured by post-treatment MRI.
4. Quality of life measures will be collected and will be compared to historically cited data.

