## STUDY SCHEMA

## STUDY CALENDAR

Procedure	Screening 	Radiosurgery Delivery	Surgical Resection	Post-Surgical Resection Visit	Follow-up  (until 18-months from post-surgical resection visit) (18 months)
Study Day/Visit Day	Day – 30 to Enrollment	Day 1	Day 2 (+8 days)	1-month ±7 days from radiosurgery	Every 3 months ±14 days
Informed Consent	X				
AE Reporting	X	X	X	X	
Concomitant Medications	X	X	X	X	X
SRS		X		X	
Physical Exam 	X			X	X
Medical History	X				
ECOG Performance Status	X			X	X
Pregnancy Test (Serum or Urine) 	X				
Neurocognitive Testing 	X				
QOL Questionnaire 	X			X	X
MRI (Brain) 	X			X	X

1. All screening procedures must occur within 30 days prior to enrollment. Treatment must start within 14 days of enrollment.
2. If a subject has disease progression/relapse or subject withdrawal, then they will be followed as per follow-up requirements.
3. Including height and weight on screening. Temperature, HR, RR, BP and O2 sats or as per institutional standards at all timepoints.
4. For women of childbearing potential, a negative pregnancy test (serum or urine) must be obtained within 30 days prior to the first study intervention.
5. Neurocognitive testing: Multilingual Aphasia Examination Controlled Oral Word Associated Test (COWAT), Trail Making Test, Parts A and B (TMT), and Hopkins Verbal Learning Test-Revised (HVLT-R).
6. QOL Questionnaire: MDASI-BT, EQ-5D-5L.
7. MRI (brain) w/ contrast. Radiographic assessments will be completed as per RANO criteria (see Appendix 3).

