## 1.5 Toxicity

Multiple studies report worsened cognitive decline and quality of life with the addition of WBRT to either SRS or surgery for a limited number of brain metastases. Given evidence for WBRT-related toxicity along with the lack of clear survival benefit with the addition of WBRT (and potentially a survival benefit with SRS alone in certain populations), the current trend for management of limited brain metastases now favors surgery (+/- postoperative SRS) or SRS alone with reservation of WBRT as a salvage option. A number of studies are now evaluating the use of SRS in patients with multiple (more than four) brain metastases. According to a recently published systematic review, SRS may be considered an option for patients with greater than four brain metastases provided the total tumor volume does not exceed 13 cc and no single metastasis is larger than 3 cc in volume. While postoperative WBRT carries the cognitive and quality of life toxicities discussed above, SRS carries the risk of CNS necrosis (up to 23%). In an effort to reduce the risk of radiation necrosis with SRS applied to larger volumes while retaining efficacy, different dose and fractionation schedules are under investigation.

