## **3.2 Design of the Current Study**

Enrolled patients will receive GK-SRS to all metastases followed by surgical resection of resectable metastases within one to 10 days following GK-SRS. Pathologic specimens will be analyzed, and the patient will enter a standard pattern of surveillance (brain MRI every three months for two years).

Quality of life will be assessed every three months, and neurocognitive evaluations will be performed every six months. These parameters will be compared to baseline testing performed at the time of enrollment. Local control, CNS progression-free survival, overall survival, rates of leptomeningeal carcinomatosis, rates of radiation necrosis, and steroid requirements will also be documented and compared with historically reported rates.

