##### Occasional, Some May Be Serious

In 100 people receiving SRS, from four to 20 may have:

- Headache
- Localized hair loss which may be permanent
- Nausea

- Vomiting
- Allergic reaction to the local anesthesia (rash, itching, nausea, or difficulty breathing)
- Bleeding and/or infection around the head frame (if a head frame is used)
- Swelling of the brain in the treated area which may require treatment with steroids
- Severe local damage to or death of normal brain tissue, which may require surgery to remove

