## **6.2 Collection and Reporting Requirements for Adverse Events and Serious Adverse Events**

### **6.2.1 Collection of Adverse Events**

All grade 3, 4, and 5 adverse events (including all SAEs) must be recorded in OnCore® and/or an adverse event log. All AEs required to be collected must be graded according to the CTCAE v5. When possible, signs and symptoms indicating a common underlying pathology should be noted as one comprehensive event. Investigator's or treating physician's assessment of AE attributions must also be documented.

AEs will be collected from the time the subject signs the consent form through 30 days post last dose of study drug(s). AEs will be tracked and followed until resolution, subject withdraws consent, or is lost to follow-up (including subjects who discontinue early). All adverse events collected per the protocol will be followed with appropriate medical management until they are resolved, if they are related to the study treatment, or until the investigator deems the event to be chronic.

Please see section 6.2.2 and table 2 to identify the adverse events that need to be reported.

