### 6.2.2 Reporting of Adverse Events and Serious Adverse Events

Please refer to table 2 below to identify adverse events that meet reporting requirements.

All serious adverse events (SAEs) that occur after the subject has signed the consent form through 30 days post last dose of study drug(s) will be reported. All SAEs will be followed until satisfactory resolution, or until the investigator deems the event to be chronic.

All serious adverse events (SAEs) must also be documented in OnCore®.

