### **Informed Consent Process**

Informed consent is a process that is initiated prior to the individual's agreeing to participate in the study and continues throughout the individual's study participation. Extensive discussion of risks and possible benefits of this therapy will be provided to the subjects and their families. Consent forms describing in detail the study interventions/products, study procedures and risks are given to the subject and written documentation of informed consent is required prior to starting intervention/administering study product.

Potential subjects will be told, and a statement will be included that this study is designed to determine both safety and effectiveness. The consent forms will include the approved MCW IRB template language.

Consent forms will be IRB approved and the subject (and legally authorized representative, if necessary) will be asked to read and review the document. The treating physician or the investigator will explain the research study to the subject and answer any questions that may arise. The study coordinator may complete the consenting process. In accordance with 46 CR 46.111, the subject will sign and date the informed consent document prior to any procedures being done specifically for the study.

A witness should only sign when required, per FH/MCW IRB policy. If a witness signs the document when not required, the study staff should document in the legal medical record (or note to file) the relationship to the patient and why a witness signed. (i.e., "Although not required, the subject's spouse was present during the consenting process and signed as the witness." Or "Although not required, hospital staff was present for consenting process and signed as a witness.")

The subjects will have the opportunity to discuss the study with their surrogates or think about it prior to agreeing to participate. The subjects may withdraw consent at any time throughout the course of the trial.

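### Radiation necrosis is sought on MRI to about month 19, but grading, attribution and SAE reporting are not required for toxicity that begins after about the first one to two months

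*Combined protocol and SAP*

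**What the plan says.** **Endpoint.** Recording necrosis is a secondary objective (Section 2.2). Section 2.4 gives the method: "Incidence of radiation necrosis will be measured by post-treatment MRI". No definition by symptoms, steroid need, reoperation, pathology or CTCAE grade is given.

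**Length of observation.** The Study Calendar schedules MRI every three months "until 18-months from post-surgical resection visit", and that visit is one month after SRS. Section 3.2 instead describes "brain MRI every three months for two years".

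**Safety window.** Section 6.2.1 collects AEs from consent to 30 days after the last dose of study drug. Section 6.2.2 applies the same limit to SAEs, namely those "that occur after the subject has signed the consent form through 30 days post last dose of study drug(s) will be reported". The calendar marks AE Reporting at screening, radiosurgery, resection and the post-surgical visit, and leaves the follow-up column empty.

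**Risk as the protocol describes it.** Section 1.5 cites CNS necrosis of up to 23% with SRS. The SRS side-effect list in Section 5.1.1 includes, among effects expected in 4 to 20 of 100 people, "Severe local damage to or death of normal brain tissue, which may require surgery to remove". Section 1.7 gives lower necrosis as part of the rationale. It cites one preoperative series with no reported necrosis and a retrospective comparison with significantly less necrosis than postoperative SRS. Under Informed Consent Process, participants are to be told that "this study is designed to determine both safety and effectiveness".

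**The concern.** The months in which the plan looks for necrosis are almost entirely months in which it does not ask for adverse events. The window fits the peri-operative period. It does not fit a toxicity that the plan itself expects to look for over 18 months or more.

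Resection does not remove the exposure. SRS goes to all metastases and only resectable ones are taken out (Section 3.2), so up to three of four irradiated lesions can stay in place. Section 5.1.2 also allows for residual disease after subtotal resection.

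Two things are at stake. First, an MRI-based incidence does not separate an incidental imaging change from necrosis that puts a patient in hospital or back in theatre, and the second is the rate that bears on the rationale. Second, enrolment is planned over about two years, so late toxicity in early patients is relevant to later ones. Under Table 2 a grade 4 event, even an expected one, goes to the DSMC within five calendar days. The same event with onset at month 6 triggers no such duty.

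**Working it through.** The plan states no figure for this point, so there is nothing to reproduce. The check is date arithmetic on its own windows, then a search for any other section that closes the gap, then the expected number of cases.

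**Conventions.** SRS is day 1 and one month is 30.44 days. The post-surgical visit is nominally day 31 ± 7, so the last visit with AE reporting falls on day 24 to 38.

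**Step 1: when the window closes.** Because there is no study drug, the starting point of the 30 days is undefined. Each reading is last intervention day + 30.

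| Last intervention taken as | Day | Window closes |
|---|---|---|
| SRS | 1 | 1 + 30 = day 31 |
| Resection, earliest | 2 | 2 + 30 = day 32 |
| Resection, latest in the calendar (day 2 + 8) | 10 | 10 + 30 = day 40 |
| Resection 10 days after SRS (Section 5.1.2) | 11 | 11 + 30 = day 41 |
| SRS mark that the calendar shows at the post-surgical visit, latest | 38 | 38 + 30 = day 68 |

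**Step 2: when follow-up ends.** 31 + 18 × 30.44 ≈ day 579, and 579 / 30.44 = 19.0 months after SRS.

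**Step 3: what is covered.** The two-year column assumes that the two years run from SRS.

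| Window closes | Share of 579 days covered | Months uncovered | Months uncovered, two-year wording |
|---|---|---|---|
| Day 31 | 31/579 = 5.4% | (579 − 31)/30.44 = 18.0 | 23.0 |
| Day 41 | 41/579 = 7.1% | (579 − 41)/30.44 = 17.7 | 22.7 |
| Day 68 | 68/579 = 11.7% | (579 − 68)/30.44 = 16.8 | 21.8 |

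**Step 4: does another section close the gap?**
- Section 4.6 continues AE and SAE reporting after treatment is discontinued, but in line with the protocol, which leads back to the 30 days.
- Section 6.2.1 follows events to resolution. That applies to events already collected, so the gap concerns onset after the window.
- Section 10.4 has CRFs document safety, completed according to the calendar, where the follow-up AE cell is blank.
- Section 8.1 has the study team review reportable SAEs. Under Section 6.2.2, later ones are not reportable.
- Section 3.2 documents steroid requirements and compares them with historical rates, without linking them to a necrosis definition or to AE reporting.
- Section 6.3 refers unanticipated problems to an institutional policy that is not in the documents.

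None of these requires a grade, an attribution or a Table 2 report for late-onset necrosis.

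**Step 5: how many cases could be involved.** Expected cases = n × p, and the chance of at least one = 1 − (1 − p)^n.

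| Assumed rate | Source | Expected, n = 10 | At least one, n = 10 | Expected, n = 15 |
|---|---|---|---|---|
| about 0 | Preoperative series, Section 1.7 | about 0 | about 0 | about 0 |
| 4% | Lower end of side-effect band | 0.4 | 34% | 0.6 |
| 20% | Upper end of side-effect band | 2.0 | 89% | 3.0 |
| 23% | Upper figure for SRS generally, Section 1.5 | 2.3 | 93% | 3.45 |

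The 4 to 20 band covers a mixed list of effects, so it is not a necrosis rate as such. These are cases at any time; the documents do not say how many would begin after the window.

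**The case against.** The strongest defence is that late necrosis is not invisible. It is a secondary endpoint, so it will be recorded. Follow-up visits also collect concomitant medications, physical examination, ECOG and quality of life, and the RANO-BM table in Appendix 3 takes in corticosteroids and clinical status. Study data go into OnCore, the DSMC reviews OnCore data, and the principal investigator reports to it twice a year. All of this stands, and it rules out several stronger readings:

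- *Late necrosis would never reach the DSMC, or the DSMC would see no late toxicity.* There is a route through OnCore and the investigator's reports. What is missing is a duty to grade, attribute and notify.
- *A late case leaves only an MRI finding, and symptomatic or steroid-requiring necrosis could not be reported.* Steroid and clinical data are collected, and such cases might be derived from them. The plan does not say that they will be. Reoperation has no evident data field, though the CRFs are not in the documents.
- *The unanticipated-problem route cannot apply because necrosis is a listed risk.* Section 6.1.4 also counts unusual severity or frequency as unexpected, so some cases might qualify. This cannot be settled without the institutional policy.
- *Necrosis is named as the main SRS toxicity.* Section 1.5 says only that SRS carries the risk.
- *Nearly all necrosis would fall outside the window.* Onset timing is not given. The uncovered share in Step 3 is scheduled calendar time, not risk or person-time, and eligibility asks only for an estimated median survival of at least six months.

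It can also be said that safety is not a named objective and that the consent statement is weak support for one. That is fair. The point rests instead on the mismatch between a stated secondary endpoint and the stated safety window.

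**Conclusion.** The point holds as a gap in required safety reporting. Sections 6.2.1 and 6.2.2 and the calendar agree with one another, so this is a stated rule and not a slip in one place. Correcting the reference to a study drug does not cure it: every reading closes the window between about day 31 and day 68, against follow-up to about day 579, which leaves about 17 to 18 months (22 to 23 under the two-year wording) without required AE or SAE collection. For necrosis or other treatment-related toxicity with onset in that time, the protocol does not require a CTCAE grade, an attribution, an SAE record or a Table 2 report.

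The number of cases affected is uncertain: about 0 to 2.3 necrosis cases in 10 patients, times an unknown share arising after the window. That any arise late is an assumption, but the gap does not depend on it, because the plan itself looks for necrosis throughout follow-up.

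**What to change.** - **Study Calendar:** mark AE Reporting at the three-monthly follow-up visits.
- **Sections 6.2.1 and 6.2.2:** count the 30-day all-cause window from the last study intervention instead of a study drug. After it, collect and report grade 3 or higher events and SAEs judged at least possibly related to SRS or resection, including radiation necrosis, to the end of follow-up, with CTCAE v5 grade, attribution and Table 2 reporting.
- **Section 2.4:** report MRI necrosis split into asymptomatic and symptomatic (by CTCAE v5 grade), using the steroid and clinical data already collected.
- **Reconcile two conflicts that affect the dates:** the 18-month calendar against the two-year surveillance in Section 3.2, and the SRS mark at the post-surgical visit against the treatment plan in Section 5.

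The cost is a little more data entry at visits that already include examination, ECOG, medications and MRI, for 10 to 15 patients, and a few more reports to the DSMC. Treatment does not change.
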